5.3 STRATEGIES FOR RECRUITMENT AND RETENTION

Study participants will be recruited with the use of an advertisement flyer to be posted locally and online. They will also be recruited by the primary investigators patient pool and general public. Any interested potential participants will contact the Primary Investigator or Study Coordinator. The participants will be informed that participation is voluntary and the decision to participate or not, will in no way affect their future care. Subsequently, the participants will be given a complete and thorough explanation of the benefits and risks or discomforts that may be anticipated with this study.

Participants will be given a monetary compensation for time and transportation in the amount of \$550.

In addition:

- The target sample size is approximately 50 participants. An anticipated number of 60-80 patients will be screened to reach the target enrollment.
- Multiple sites will be used to recruit participants to be enrolled from the U.S.
- Source of participants will come from the primary investigators patient pools as well as the general public.
- Recruitment venues will include advertisement/flyer posting
- Advertisements will include local flyers

5.4 PARTICIPANT WITHDRAWAL OR TERMINATION

Participants are free to withdraw from participation in the study at any time upon request. An investigator may terminate participation in the study if:

- Any clinical adverse event (AE), laboratory abnormality, or other medical condition or situation occurs such that continued participation in the study would not be in the best interest of the participant
- The participant meets an exclusion criterion (either newly developed or not previously recognized) that precludes further study participation.]

Data for patients lost to follow up/withdrawal will be collected if possible. Subjects in the ITT population but not in the mITT group will be represented in all tables except those for the primary and secondary endpoint analysis. Data from those withdrawing from or lost to follow-up in the mITT population will be used for the primary endpoint and, if there is at least one full day's worth of data on the number of SUI episodes available, then this subject will also be included in the analysis of change in number of SUI episodes. Attempts will be made to contact subjects withdrawing from or lost to follow-up to the mITT population to administer the QoL questionnaire. If successful these subjects will be included in the change in QoL analysis. For mITT subjects not completing the treatment phase, a "last observation carried forward" approach will be used (see section 10 "Statistical Considerations"). If it appears that there will not be 50 subjects in the PP population further recruitment and enrollment will be necessary.

5.5 PREMATURE TERMINATION OR SUSPENSION OF STUDY

This study may be temporarily suspended or prematurely terminated if there is sufficient reasonable cause. Written notification, documenting the reason for study suspension or

termination, will be provided by the suspending or terminating party to <investigator, funding agency, the IND/IDE sponsor and regulatory authorities>. If the study is prematurely terminated or suspended, the PI will promptly inform the IRB and will provide the reason(s) for the termination or suspension.

Since this study is a non-significant risk study, there are no stopping rules required.

Circumstances that may warrant termination or suspension include, but are not limited to:

- Determination of unexpected, significant, or unacceptable risk to participants
- Insufficient compliance to protocol requirements

Study may resume once concerns about safety, protocol compliance, and data quality are addressed and satisfy the sponsor, IRB and FDA.

6 STUDY AGENT

6.1 STUDY AGENT(S) AND CONTROL DESCRIPTION

The study devices will be provided by the sponsor and delivered to the investigator. Device accountability and distribution records will be maintained. The product will be packaged to prevent contamination. The PI will be trained by Rinovum Subsidiary 2, LLC. personnel on device placement for the screening visit fit assessment. Participants will not be trained on how to use the device since the indications for use are OTC. They will be given the IFU and instructed to demonstrate insertion and removal under physician supervision to verify that they successfully completed the steps. The fit assessment will include participant input to demonstrate proper understanding of whether or not the device is appropriate for her.

The manufacturer of the device is Rinovum Subsidiary 2, LLC. Design Controls and Good Manufacturing Procedures shall be used in the manufacturing of the device, in accordance with 21 CFR part 820. The PI will give the participants 42 preweighed pads for the duration of the study. The PI will give participants 20 SUI devices. Participants will complete the baseline first wearing only preweighed pads and then complete the treatment phase, where participants will wear both a preweighed pad and an SUI device.

The SUI devices consist of the following:

- Device size(s): One size (Quantity: 20)
- Device model(s): SUI Pessary Device, Disposable, Single Use
- Preweighed pads will be provided to the participant (quantity: approximately 42)
- Duration of Use: The device will be used for a period of 12 hours
- Frequency of use: 14 consecutive days
- Double ziplock bags and shippers for mailing used pads to the study site for weighing

The storage and shelf life requirements for the Rinovum Subsidiary 2, LLC SUI Pessary device are as follows:

The device is made of plastic-like and silicone-like materials. These materials have a long history of use and have been shown not to deteriorate over time.

6.2 STUDY AGENT ACCOUNTABILITY PROCEDURES

A Device Accountability Form shall be used to document the following:

- Reconciliation of investigational device accountability;
- Verify that the device accountability documentation is accurate and complete;
- Arrange for return of all unused devices and clinical supplies to Rinovum Subsidiary 2, LLC. as applicable.

7 STUDY PROCEDURES AND SCHEDULE

This study will include the following procedures:

- Medical history
- Fit assessment to ensure that device is a proper fit and does not prevent voluntary voiding
- Physical examination (vital signs, height, weight, vaginal exam for vaginal infection evaluation)
- Vaginal swab to evaluate vaginal microflora
- Urinalysis to check for active urinary infection
- Urine Pregnancy Test (if applicable)
- Participants will be given an IFU and demonstrate insertion and removal of device under physician supervision
- Distribution of preweighed pads for the baseline phase
- Distribution of preweighed pads and devices for the treatment phase
- Return via mail all worn pads for weight recording
- Collection of study diaries, to be completed at home by the participant
- Quality of Life Questionnaire

7.2 LABORATORY PROCEDURES/EVALUATIONS

A urine pregnancy test, if applicable, will be performed no more than 24 hours prior to study intervention. A urinalysis will be performed to ensure no infections are active at the time of screening and at the end of treatment phase. Results of both urine pregnancy test and urinalysis test shall be made available prior to administration of study product.

A vaginal swab shall be obtained at the time of enrollment, before treatment phase, and after end of treatment phase to evaluate any changes in vaginal microflora.

7.3 STUDY SCHEDULE

Prior to enrollment, screening questions, a medical file review, a physical examination, pregnancy test (if applicable), urinalysis, and a human factors and a fit assessment will be used to determine/assess whether a participant meets the eligibility criteria. A vaginal swab shall be performed to establish baseline vaginal microflora. These activities must be performed within 1 week of enrollment. Informed consent will be obtained prior to any screening procedures. The human factors and fit assessment will include the following:

- Participant will perform self-insertion and removal in accordance with the IFU under supervision of physician
- Participant will provide feedback regarding the fit of the device based on the IFU description of proper fit without input of the physician
- Physician will verify device is a proper fit for participant after participant performs self-insertion (if physician determines the device is not a good fit for the participant, the participant may be terminated from the study)

Enrollment/Visit #1 schedule shall consist of the following:

- Provide participants with a description of what to expect with the study
- Participant will complete a Quality of Life Survey
- Provide the patient with a Baseline Study Diary for them to keep track of their leaking patterns for the first phase of the study
- Physician will administer 14 preweighed pads for the patient to wear for 7 consecutive days.
- Record any adverse events

NOTE: all worn pads will be placed in preweighed, double sealed, ziplock bags and returned to the clinical site via mail within 48 hours of use by the participant for weighing throughout the entirety of the study

NOTE: to minimize time between pad wearing and pad weighing, participants will be mailing back all worn pads immediately upon completion of the 7-day wear to the site. The site will record the pad weights in the Pad Weight Log form.

Visit #2 schedule shall consist of the following:

- Update Medical History, if applicable
- Perform a urine pregnancy test, if applicable
- Perform a vaginal swab for vaginal microflora assessment
- Assess for any symptoms of active vaginal infections requiring treatment (if a patient is symptomatic of a vaginal infection, they may be treated and enrolled at a later date once vaginal infection has resolved).
- Collect Baseline Study Diary from participant
- Go over a series of questions with participants
- Repeat the Quality of Life questionnaire
- Administer the Treatment Study Diary
- Physician will administer 20 devices and 28 preweighed pads to wear both device and pad simultaneously for 14 consecutive days.
- Record any adverse events

NOTE: to minimize time between pad wearing and pad weighing, participants will be mailing back all worn pads immediately upon completion of every 7-day wear to the site. The site will record the pad weights in the Pad Weigh Log form. If the participant returns for Visit #3 within 2 days of completing the 14-day wear, they may bring the remaining 7 worn pads to the visit in lieu of mailing in pads at the physician's discretion.

Visit #3 schedule shall consist of the following:

- Update Medical History, if applicable
- Perform a urinalysis and vaginal microflora swab
- Assess for any active vaginal infection
- Collect and review the Treatment Study Diary
- Collect and weigh any remaining worn pads, if applicable
- Complete the Final Questionnaire
- Complete the post-treatment Quality of Life Survey
- Record any adverse events

Procedures	Screening	Enrollment/ Baseline (Visit 1) ¹	Follow-Up (Visit 2)	Follow-Up (Visit 3)
Informed consent	X			
Demographics	X			
Medical history	X	X	X	X
Physical exam	X			X
Vital signs	X	X	X	X
Height	X			X
Weight	X			X
Human Factors and Fit Assessment	X			
Urine Pregnancy Test (if applicable)	X		X	
Urinalysis	X			X
Administer Investigational Product			X	
Adverse event evaluation		X	X	X
Vaginal swab	X		X	X
Questionnaire	X	X	X	X
Quality of Life Survey		X	X	X

(1) Enrollment must be take place within 1 week of screening. Otherwise, screening procedures must be repeated prior to enrollment

7.4 CONCOMITANT MEDICATIONS, TREATMENTS, AND PROCEDURES

Prescription medications taken during study participation will be recorded on the case report forms (CRFs). For this protocol, a prescription medication is defined as a medication that can be prescribed only by a properly authorized/licensed clinician. Medications to be reported in the CRF are concomitant prescription medications, over-the-counter medications and non-prescription medications. This information shall be collected during the medical history collection. There are no known concomitant medications for the treatment of SUI. However, concomitant treatments include pelvic floor strengtheners, such as Apex, biofeedback treatments, and physical therapy for SUI.

7.5 JUSTIFICATION FOR SENSITIVE PROCEDURES

There are no drug or food interactions for this study. Participants should not use the device while using a tampon, diaphragm, or other vaginal device.

7.6 PROPHYLACTIC MEDICATIONS, TREATMENTS, AND PROCEDURES

Not applicable.

7.7 RESCUE MEDICATIONS, TREATMENTS, AND PROCEDURES

Not applicable.

7.8 PARTICIPANT ACCESS TO STUDY AGENT AT STUDY CLOSURE

Participants will not have continued access to the study agent at study closure.

8 ASSESSMENT OF SAFETY

8.1 SPECIFICATION OF SAFETY PARAMETERS

An adverse event means any untoward medical occurrence associated with the use of an intervention in humans, whether considered intervention-related (21 CFR 312.32 (a)).]

A Serious adverse event (SAE) is defined as an AE or suspected adverse reaction is considered "serious" if, in the view of either the investigator or sponsor, it results in any of the following outcomes: death, a life-threatening adverse event, inpatient hospitalization or prolongation of existing hospitalization, a persistent or significant incapacity or substantial disruption of the ability to conduct normal life functions, or a congenital anomaly/birth defect. Important medical events that may not result in death, be life-threatening, or require hospitalization may be considered serious when, based upon appropriate medical judgment, they may jeopardize the patient or participant and may require medical or surgical intervention to prevent one of the outcomes listed in this definition.

An unanticipated adverse device effect (UADE) is defined any serious adverse effect on health or safety or any life-threatening problem or death caused by, or associated with, a device, if that effect, problem, or death was not previously identified in nature, severity, or degree of incidence in the investigational plan or application (including a supplementary plan or application), or any other unanticipated serious problem associated with a device that relates to the rights, safety, or welfare of participants (21 CFR 812.3(s)).

8.2 CLASSIFICATION OF AN ADVERSE EVENT

All AEs will be assessed by the PI using a protocol defined grading system. Describe the method of grading an AE for severity. For example, many toxicity tables are available for use and are adaptable to various study designs.

The following guidelines will be used to describe severity.

- **Mild** – Events require minimal or no treatment and do not interfere with the participant's daily activities.
- **Moderate** – Events result in a low level of inconvenience or concern with the therapeutic measures. Moderate events may cause some interference with functioning.
- **Severe** – Events interrupt a participant's usual daily activity and may require systemic drug therapy or other treatment. Severe events are usually potentially life-threatening or incapacitating.

The PI's assessment of an AE's relationship to study device is part of the documentation process, but it is not a factor in determining what is or is not reported in the study. If there is any doubt as to whether a clinical observation is an AE, the event should be reported. All AEs must have their relationship to study agent assessed. In a clinical trial, the study product must always be suspect. To help assess, the following guidelines are used.

- **Related** – The AE is known to occur with the study agent, there is a reasonable possibility that the study agent caused the AE, or there is a temporal relationship between the study agent and event. Reasonable possibility means that there is evidence to suggest a causal relationship between the study agent and the AE.
- **Not Related** – There is not a reasonable possibility that the administration of the study agent caused the event, there is no temporal relationship between the study agent and event onset, or an alternate etiology has been established.

The PI will be responsible for determining whether an AE is expected or unexpected. An AE will be considered unexpected if the nature, severity, or frequency of the event is not consistent with the risk information previously described for the study agent.

The PI will record all reportable events with start dates occurring any time after informed consent is obtained until 7 (for non-serious AEs) or 30 days (for SAEs) after the last day of study participation. At each study visit, the investigator will inquire about the occurrence of AE/SAEs since the last visit. Events will be followed for outcome information until resolution or stabilization.

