10.8 Adverse Events

No formal testing of adverse events or their characteristics will be performed. Reporting is described above. The latest version of MedDRA will be used for coding. The section of tables will include a summary table, a system organ class/preferred term table, and tables for relationship and severity to study treatments.

10.9 Interim Analyses and Stopping Criteria.

No interim analyses are planned, and the study will be run to its completion unless stopped for safety considerations.

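### The Related and Not Related classes in section 8.2 overlap with no precedence rule, so the relationship table in section 10.8 is not consistently defined across sites

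*Combined protocol and SAP*

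**What the plan says.** Section 8.2 makes causality assessment compulsory: "All AEs must have their relationship to study agent assessed". It then offers two classes.

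- *Related* has three alternatives. The first two are "The AE is known to occur with the study agent, there is a reasonable possibility that the study agent caused the AE"; the third is "or there is a temporal relationship between the study agent and event".
- *Not Related* also has three. The first is "There is not a reasonable possibility that the administration of the study agent caused the event"; the other two are "there is no temporal relationship between the study agent and event onset, or an alternate etiology has been established".

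Just before the definitions stands a general principle: "In a clinical trial, the study product must always be suspect". The same section limits what the assessment is used for, saying that "it is not a factor in determining what is or is not reported in the study".

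Section 10.8 plans no formal testing of adverse events. Its named outputs are a summary table, a table by system organ class and preferred term, and "tables for relationship and severity to study treatments". Section 4.3 makes the evaluation of adverse events secondary endpoint (3). The Protocol Summary gives 4 enrolling sites.

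**The concern.** Two classes that are meant to divide the events should not both be satisfied by the same event. Here they can be, and the text does not say what the investigator should do then. Two sites could classify identical events differently and both be following the protocol.

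The exposed events are ones the protocol expects. Section 2.3 lists urinary tract infection, vaginal infection, irritation and spotting among the device's risks. All of these can also arise without it.

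The trial has a single arm, so no concurrent group shows the background rate. Recording starts at consent (section 8.2), and the safety population is everyone who receives a control-phase pad (section 4.2), so events from the pad-only week are counted too. Section 10.8 names no split by control and device phase. That leaves the relationship table as the only named adverse event output that separates device-attributable events from background events, and section 8.6 describes no central adjudication of causality.

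**Working it through.** The plan states no figure that depends on these definitions, so there is none to reproduce. The check is one of logic.

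**Inputs (section 8.2).** Describe each event by four yes/no attributes, which gives 2 × 2 × 2 × 2 = 16 combinations:
- K: known to occur with the device
- P: reasonable possibility that the device caused it
- T: temporal relationship to the device
- A: another cause has been established

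**Rules as written**
- *Related* = K or P or T
- *Not Related* = (not P) or (not T) or A

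**Events during device wear (T = yes).** *Related* is always met. *Not Related* reduces to (not P) or A.

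| P | A | Classes met |
|---|---|---|
| no | no | both |
| no | yes | both |
| yes | yes | both |
| yes | no | *Related* only |

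Each row occurs twice (K = yes, K = no). So 6 of 8 combinations meet both classes, 2 meet only *Related*, and none meets only *Not Related*.

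**Events with no temporal link (T = no), such as most of the pad-only week.** *Not Related* is always met. *Related* is met if K or P is yes, which is 3 of the 4 (K, P) pairs. With two values of A, that is 6 of 8 meeting both and 2 meeting only *Not Related*. A control-week urinary infection, for example, can be *Related* as a known effect and *Not Related* on timing. (Events linked in time to the insertion test at screening would fall under T = yes.)

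**Total as written:** 6 + 6 = 12 of 16 meet both.

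**Other readings of *Not Related***
- If the first two alternatives must hold together, so that the rule is (not P and not T) or A, 8 of 16 meet both. With T = yes it is 4 of 8, namely every combination with an established other cause.
- If all three must hold together, 0 of 8 with T = yes meet both. But this reading replaces the written *or*, makes every device-phase event *Related*, and still leaves 1 of 16 combinations in both classes and 1 in neither.

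These are counts of logical combinations, not event frequencies, and some combinations will be rare in practice.

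**Sensitivity of the table.** With the expected safety population of 60 to 70, each woman whose only events meet both classes moves the share with a related event by 100/70 = 1.4 to 100/60 = 1.7 percentage points. The documents do not say how many such women to expect.

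**Check of the proposed rule.** *Not Related* = (not P) and [(not T) or A]; everything else is *Related*. With P = no, three of the four (T, A) pairs qualify, and K doubles this to 6. So 6 of 16 are *Not Related*, 10 are *Related*, and none falls in both or neither.

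**The case against.** The best reply is that section 8.2 already tells the assessor where to lean, since the product is always to be suspected. That is a principle and not an order of precedence. Used as a tie-break that always favours *Related*, it would classify every device-phase event as *Related*, because no combination with T = yes meets *Not Related* alone. The other-cause clause would then do nothing where it matters most.

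A second reply is that these are guidelines to help a clinician. Section 8.3 limits causality assessment to people with the training and authority to diagnose, and section 9 plans audits for consistency across sites. This is fair, and good judgement will settle many cases. But these are the only criteria given, every event must be classified, and an audit cannot find a deviation where two answers both fit the text.

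A third reply is that little hangs on it, and most of this stands. Reporting does not depend on relationship (section 8.2), all events are documented whatever the relationship (section 8.3), serious events go to the sponsor regardless of it (section 8.4), and no test uses it (section 10.8).

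Some stronger readings are tempting but unsupported:
- A reader might infer that any plausible other cause allows *Not Related* through the last clause. The text requires that the cause be established.
- A reader might infer that an open-label design pushes classification towards *Not Related*. Nothing in the documents shows this, and the one directional statement points the other way.
- A reader might treat a device-related event rate as the main safety result. No such endpoint or threshold is defined. Section 3 bases safety on all adverse events, including the urinalysis, swab and examination results, and section 10.4 makes safety reporting descriptive and narrative.

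**Conclusion.** The point holds as a contradiction between two stated definitions. An event during device wear with an established other cause meets both classes, and a control-phase event of a known type can too. The first overlap survives every reading that keeps the final *or* in the *Not Related* definition.

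The consequence is confined to one descriptive output: the relationship table is not a consistently defined quantity across the 4 sites. Its size and direction cannot be calculated, because the documents give no adverse event rates and no expected number of events meeting both classes. Total adverse event counts, submission of serious events and all inference stand as planned. The conclusion assumes that the definitions are applied as printed and that no further site instruction outside these documents sets an order of precedence.

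**What to change.** Replace both bullets in section 8.2, rather than adding to them, with classes that are exclusive and exhaustive. For example: *Not Related requires no reasonable possibility of a causal link, and in addition either no temporal relationship or an established other cause; every other event is Related.* Repeat the rule in the instructions for the adverse event form so that all sites apply it alike. This should be done before sites classify events, because an analysis plan written later could repair the table only by reclassifying them.

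In section 10.8, add a table of all-cause adverse events by phase (control versus device) and place it ahead of the relationship table. It does not depend on attribution, and onset time is already collected under section 8.3, so no new data are needed.

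The cost is a short protocol edit, a form note and one more descriptive table. The related count may come out somewhat higher, since a device-phase event without an established other cause could no longer be classed as *Not Related*.
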